6.5 POOLING OF CENTRES

Not applicable because centre/country is not included in the statistical

6.6 HANDLING OF MISSING DATA AND OUTLIERS

If not stated otherwise, missing data will not be imputed and remain missing. Potential outliers will be reported and analysed as observed.

Missing or incomplete AE dates are imputed according to BI standards [\(4\)](#).

A large rectangular area of the page has been completely blacked out, indicating the redaction of sensitive information.

For missing laboratory data at Visit 1 (before the very first administration of study medication) data from preceding visits will be used.

6.7 BASELINE, TIME WINDOWS AND CALCULATED VISITS

Study days and visits will be labelled according to the CTP's flow chart.

Unless otherwise specified, baseline is defined as the time-point closest to but prior to first administration of trial medication in course 1. Note that for some trial procedures (for example body weight, vital signs, laboratory tests) this may be the value measured on the same day trial medication was started. In these cases it will be assumed that the

measurements were taken according to protocol, i.e. prior to first intake of any trial medication.

Laboratory values: Baseline is defined as the latest time-point before the very first administration of any trial medication in course 1. For laboratories where not only the examination date but also time are recorded, examination time has to be taken into account when defining baseline. That is, a laboratory value on the same date as the first trial drug administration is considered as baseline value if and only if the time of laboratory value is before or the same as the time of first trial drug administration.

7. PLANNED ANALYSIS

The labelling and display format of statistical parameters will follow the guideline “Reporting of Clinical Trials and Project Summaries” [\(7\)](#).

For End-Of-Text (EoT) tables, the set of summary statistics is: N / Mean / Standard deviation (SD) / Min / Median / Max.

For tables that are provided for endpoints with some extreme data, median, quartiles and percentiles will be preferred to mean, standard deviation, minimum and maximum.

In general, means, medians, SD and percentiles will be presented to one more decimal place than the raw data. Minima and maxima will be presented to the same number of decimal places as the raw data.

Tabulations of frequencies for categorical data will include all possible categories (even if with no count and also the missing category if there is missing data) and will display the number of observations in a category as well as the percentage (%) relative to the number of subjects in the respective treatment group (unless otherwise specified, all subjects in the respective subject set whether they have non-missing values or not). Percentages will be rounded to one decimal place. The category missing will be displayed only if there are actually missing values.

If a table presents only categorical data, “N (%)” will be displayed in the column header only.

Abbreviations (e.g., Wors.) or acronyms (e.g., PD) will not be displayed in tables and Subject Data Listings (SDLs) without any explanation. They will be either spelled out or explained in footnotes.

If applicable, conversion from days to weeks, months and years will be as follows:

- Weeks = days \div 7
- Months = $12 \times$ days \div 365.25
- Years = days \div 365.25

7.1 DEMOGRAPHIC AND OTHER BASELINE CHARACTERISTICS

Standard descriptive analyses and summary tables are planned for this section of the report. Data will be summarized by treatment group and a “total” column will be included in the summary tables.

Body Surface Area (BSA):

$$\text{BSA}[\text{m}^2] = 0.007184 \times \text{height}[\text{cm}]^{0.725} \times \text{weight}[\text{kg}]^{0.425}$$

Time from first diagnosis [months] = (date of informed consent - date of first diagnosis +1)[days]×12/365.25

7.2 CONCOMITANT DISEASES AND MEDICATION

Only descriptive statistics are planned for this section of the report.

Concomitant diseases will be coded similarly as adverse events based on the most current Medical Dictionary for Regulatory Activities (MedDRA®) version. Concomitant therapies (CTs) will be coded according to WHO DD. CTs will be classified according to the Anatomical, Therapeutic, Chemical (ATC) classification system. The third ATC level will be used to categorize CTs by therapy type. In situations where a medical product may be used for more than one equally important indication, there are often several classification alternatives. As appropriate, subjects receiving CTs with more than one possible ATC level-three category will be counted more than once; footnotes will clarify this possible double counting in tables.

7.3 TREATMENT COMPLIANCE

Only descriptive statistics are planned for this section of the report.

7.4 PRIMARY ENDPOINT(S)

Phase I

The primary endpoints are the MTD and the occurrence of DLT. The MTD is determined from the number of non-replaced subjects with DLT during the MTD evaluation period.

The MTD evaluation period is defined as the time from the first administration of study treatment to the start of the second treatment cycle or the end of the 30-day residual effect period after the last drug administration, whichever comes first. Subjects who were replaced during the MTD evaluation period are not considered for MTD determination. Those subjects who have completed the MTD evaluation period without having been replaced are referred to as subjects evaluable for MTD.

An overall summary of subjects with DLT(s) which occurred during the MTD evaluation period and the on-treatment period will be provided for each dose cohort.

Subjects who were treated but replaced are not considered for the MTD determination.

However, all information, including adverse events qualifying for a DLT from later times, will be considered in the final determination of the recommended Phase II dose (RP2D).

In order to describe the occurred dose escalation steps, a listing of all treated subjects will be provided. This will include the initial dose of the investigational medicinal product, subject number, treatment start date, DLT in MTD evaluation period [y/n], Evaluable for MTD [y/n] and will be sorted by treatment start date.

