All withdrawals will be documented and the reason for withdrawal recorded. As soon as a patient is withdrawn from the trial treatment, the End of Treatment (EOT) visit and the End of Residual Effect Period (REP) visit (EoR visit) have to be performed if feasible. Every effort should be made to follow-up with patients in case an adverse event (AE) is still ongoing at the time of withdrawal. If a patient is withdrawn from the trial due to documented full consent withdrawal (i.e. withdrawal from both, trial treatment and trial participation), no further visits will be completed and no further trial data will be collected. However, if

information about survival status is publicly available, then the Investigator is requested to report this information in the eCRF.

A patient has to discontinue trial drug administration, i.e. both BI 836858 and decitabine, in case:

- a DLT occurs which does not recover to a degree that allows treatment continuation (see [Section 4.1.4](#)).
- development of progressive disease (PD) or any other concomitant diagnosis including deterioration of general condition develops resulting in an indication to start any other therapy for AML.

Patients who have not completed at least 3 administrations of BI 836858 during cycle 1 due to BI 836858-related toxicity will not be replaced; this will be considered as a DLT. However, patients who have not completed at least 3 administrations (1 cycle) of BI 836858 for reasons other than BI 836858-related toxicity will be replaced.

Patients who experienced DLT but have subsequently recovered and are able to resume trial treatment will be allowed to continue on trial treatment, as long as criteria for further treatment are met ([Section 4.1.4.1](#)).

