5.3.1 Dose limiting toxicity (DLT)

DLT is defined as any non-disease-related non-hematological AE of CTCAE grade 3 or higher.

Expected non-hematological disease-related AEs will not be regarded as a DLT. These include complications resulting from hematological AEs such as:

- Bleeding and complications from bleeding due to thrombocytopenia as defined by the Investigator
- Infection and complications from infections due to neutropenia as defined by the Investigator
- Constitutional symptoms due to anaemia as defined by the Investigator

Infusion-related reactions (IRR) associated with the administration of BI 836858 should be reported as Adverse Event of Special Interest (AESI, refer to [Section 5.3.8.1](#)), but will not be regarded as a DLT. The exception is anaphylaxis which occurs despite premedication with glucocorticoid or which does not resolve with glucocorticoid (i.e. such cases of anaphylaxis will be regarded as a DLT).

Patients who do not receive at least 3 administrations of BI 836858 due to BI 836858-related toxicity are considered to have developed a DLT. If Cycle 2 is not started until 57th day from Day 1 of Cycle 1 as a result of drug-related AE, this AE is considered as DLT (i.e. treatment delay of \geq 4 weeks of the start of Cycle 2 due to drug-related AE). Patients who do not experience a DLT but do not receive all 3 planned administrations of BI 836858 during Cycle 1 for reasons other than toxicity or tolerability will not be evaluable for DLT and cannot be used to establish the MTD.

Infection will not constitute a DLT unless it is felt that the infection resulted from unexpectedly complicated myelosuppression; degree of severity and/or duration as assessed by the Investigator.

Since patients with refractory leukemia have infections and bleeding complications from myelosuppression, these events will not be considered as DLT unless they occur in the setting of prolonged myelosuppression from the combination treatment. Prolonged myelosuppression is defined as ANC < 1000/ μ L and PLT < 100,000/ μ L by day 56 of Cycle 1 in the setting of bone marrow showing < 5% blasts, without evidence of persistent cytogenetic abnormalities or minimal residual disease by flow cytometry. In case persistent cytogenetic abnormalities or immunophenotypic evidence of leukemia is present, myelosuppression would be considered secondary to leukemia even if morphology shows < 5% blasts.

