5. ENDPOINTS(S)

5.1 PRIMARY ENDPOINT(S)

Phase I

The primary endpoints in the Phase I part of the trial are the maximum tolerated dose (MTD) and the number of subjects with of dose limiting toxicity (DLT) during the MTD evaluation period.

Maximum tolerated dose (MTD):

The MTD is defined as the highest dose of BI 836858 (in combination with decitabine) with less than 25% risk of the true DLT rate being above 33% during the MTD evaluation period.

MTD evaluation period:

The MTD evaluation period is defined as the time from the first administration of study drug to the start of the second treatment cycle or the end of 30-day residual effect period after last administration of study drug, whichever comes first. Subjects who were replaced during the MTD evaluation period will not be considered for MTD determination. The subjects who are completed the MTD evaluation period without being replaced are considered MTD evaluable.

In case a subject has not completed the required number of administrations due to BI 836858 related toxicity, he/she will not be replaced and this will be considered as DLT. However, subjects who have not completed the required number of administrations of BI 836858 for reasons other than BI 836858 related toxicity will be replaced. Subjects who were replaced during the MTD evaluation period will not be considered for MTD

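### SAP 5.1 and 7.4 leave every replaced patient out of the MTD with no exception for a DLT, so, read literally, a protocol DLT not attributed to BI 836858 can be lost from the primary estimate

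*SAP*

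**What the plan says.** Four places bear on who counts towards the MTD.

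- **SAP 5.1 and 7.4, exclusion.** SAP 7.4: "Subjects who were replaced during the MTD evaluation period are not considered for MTD determination". SAP 5.1 has the same rule, and 7.4 takes the MTD from DLTs in non-replaced subjects. SAP 5.1 defines the MTD as the highest dose with "less than 25% risk of the true DLT rate being above 33% during the MTD evaluation period".
- **Protocol 3.3.4.1, replacement.** "patients who have not completed at least 3 administrations (1 cycle) of BI 836858 for reasons other than BI 836858-related toxicity will be replaced". SAP 5.1 carries the same trigger. Its one protected case is a patient stopped by BI 836858-related toxicity: "he/she will not be replaced and this will be considered as DLT".
- **Protocol 5.3.1, DLT and evaluability.** "DLT is defined as any non-disease-related non-hematological AE of CTCAE grade 3 or higher". Attribution to BI 836858 is not part of that definition. The evaluability rule is narrow. Its subject is "Patients who do not experience a DLT but do not receive all 3 planned administrations of BI 836858 during Cycle 1". Of these, only the ones whose doses were missed "for reasons other than toxicity or tolerability will not be evaluable for DLT and cannot be used to establish the MTD".
- **SAP 6.3, MTD evaluable set.** It combines patients who completed the first planned cycle with a second group tied to at least 2 doses, BI 836858-related toxicity and non-replacement. That sentence does not parse, and its count of 2 differs from the 3 administrations in protocol 3.3.4.1 and 5.3.1.

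**The concern.** Replacement turns on whether the missed dose was due to BI 836858-related toxicity. Evaluability in protocol 5.3.1 turns on whether the patient had a DLT and, if not, whether doses were missed for any toxicity or tolerability reason. The two tests part for a patient with a grade 3 or higher non-haematological event attributed to decitabine, or to neither drug, who then receives fewer than 3 administrations. Protocol 5.3.1 counts that patient as a DLT. Protocol 3.3.4.1 replaces the patient, and SAP 5.1 and 7.4 then remove whoever was replaced.

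The path is plausible. Protocol 4.1.4.3 holds both drugs after a DLT, and protocol 4.1.4 records an infusion outside its window as missed, so the DLT can itself cause the missed administration. The MTD evaluation period also starts with the first dose of either drug (SAP 3 and Table 6.1:1), about a week before BI 836858 begins.

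At stake is the direction of error. Removing a patient with a DLT lowers the estimated risk at that dose and can let it meet the 25% limit.

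**Working it through.** **Step 1: the rules applied to one patient.** Take a treated patient with a protocol DLT attributed to decitabine and only 2 BI 836858 administrations.

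| Text | Result |
|---|---|
| Protocol 5.3.1 | DLT; the non-evaluability sentence does not apply |
| Protocol 3.1 and 4.1.3.1 | a patient with a DLT has met the cohort-completion condition |
| Protocol 3.3.4.1, SAP 5.1 | replaced, if the missed dose is not due to BI 836858-related toxicity |
| SAP 5.1, 7.4 | not considered for the MTD |

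**Step 2: rebuild the model.** Inputs are the protocol 7.1.1 equations, the Table 7.1.1:3 mixture priors (weights 0.9 and 0.1), the interaction prior N(0, SD 0.993), and reference doses of 160 mg and 20 mg/m². For each drug, logit(p) = log(alpha) + beta × log(dose/reference). Then p0 = p1 + p2 − p1·p2, and odds(p) = odds(p0) × exp(eta × d1/160 × d2/20). Prior draws are weighted by the binomial likelihood. P(OD) is the posterior probability that p is at least 0.33.

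**Step 3: reproduce the plan's figures** (Tables 7.1.1:4 and 10.2:1).

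| Data | P(OD) at | Published | Recomputed |
|---|---|---|---|
| Prior | 20 / 40 / 80 / 160 mg | 0.133 / 0.186 / 0.312 / 0.537 | 0.135 / 0.190 / 0.312 / 0.538 |
| 1/3 at 20 mg (scenario 2.1) | 20 mg | 0.153 | 0.151 |
| same | 40 mg | 0.222 | 0.226 |
| 2/3 at 20 mg (scenario 3.1) | 20 mg | 0.417 | 0.416 |
| 1/3 at 40 mg (scenario 2.2) | 40 mg | 0.204 | 0.204 |
| 0/3 at 20, 2/3 at 40 mg (scenario 6) | 40 mg | 0.291 | 0.285 |

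All agree within 2 percentage points. Scenario 5 at 80 mg (published 0.244, recomputed 0.259) falls on opposite sides of 0.25, so nothing here rests on it.

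**Step 4: keep or drop one DLT patient.** A DLT-free replacement has joined, so r/n when dropped becomes (r+1)/(n+1) when kept. The data are assumed, not trial results.

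| Data | Kept | P(OD) | Dropped | P(OD) | Crosses 25%? |
|---|---|---|---|---|---|
| 20 mg only | 2/4 | 0.305 | 1/3 | 0.151 | yes |
| 40 mg only | 2/4 | 0.383 | 1/3 | 0.204 | yes |
| 0/3 at 20, 1/6 at 40, then 80 mg | 3/7 | 0.359 | 2/6 | 0.216 | yes |
| 0/3 at 20, 1/6 at 40, then 80 mg | 2/7 | 0.168 | 1/6 | 0.079 | no |
| 0/3 at 20, then 40 mg | 2/4 | 0.218 | 1/3 | 0.103 | no |
| 0/3 at 20, 40 and 80, then 160 mg | 2/4 | 0.541 | 1/3 | 0.301 | no |

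The third decimal varies by about 0.001 between runs. The two 80 mg rows use 3 + 6 + 7 = 16 patients when kept, the dose-escalation number in the protocol synopsis. The layout is assumed because the cohort doses are redacted. It meets the overdose criterion at each step.

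In the first row, dropping the DLT leaves 40 mg permitted (0.226). Keeping it gives 0.402 at 40 mg, so no listed dose qualifies. If the dropped DLT is the only one (1/4 against 0/3 at 20 mg), P(OD) at 40 mg is 0.177 against about 0.08, and 40 mg is permitted either way.

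**The case against.** The best defence is that the case never arises. Protocol 3.1 and 4.1.3.1 close a cohort once each patient has had a DLT or been observed for Cycle 1, so a patient with a DLT already counts and needs no replacement. Protocol 5.3.1 points the same way. This is a reasonable account of intent, and it stands as one of two readings. It does not override protocol 3.3.4.1, which states its replacement rule without an exception for patients who had a DLT, or the SAP, which adds none. It is also fair that the replacement trigger originates in the protocol; the SAP adds the blanket exclusion.

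The loss would not be hidden. SAP 7.4 plans a DLT summary by cohort and a listing of DLT and evaluability for every treated patient, and considers all information for the RP2D. Protocol 7.3.1 adds a model re-run with DLTs from all cycles. These disclose an exclusion but do not restore the patient to the MTD as the SAP defines it.

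Four stronger inferences are not supported.

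- **That the reported MTD is wrong, or that the SAP deliberately changed the rule.** No affected patient is documented, and SAP section 4 records only the Phase II cancellation.
- **That the exclusion contradicts the decitabine prior.** The notes to Table 7.1.1:2 say which historical events were counted, not who is evaluable in this trial.
- **That a frequency can be given.** The historical counts, 7/50 + 3/25 + 7/53 = 17/128, approximate DLTs from adverse events; one study includes events possibly due to valproic acid and another covers two cycles. The share of such patients who would miss doses and be replaced is unknown.
- **That SAP 6.3 drops patients stopped early by BI 836858-related toxicity.** Read literally it omits one stopped after a single administration, but SAP 5.1 counts that patient as a DLT and the visible text of 7.4 does not name the 6.3 set. This is a wording conflict only.

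**Conclusion.** The concern holds as a conflict in the current text. Protocol 5.3.1 counts a DLT whatever drug it is attributed to, while the replacement rule followed by the SAP exclusion can remove that patient from the primary MTD estimate. The error would run one way, towards a lower estimated risk. One dropped DLT can decide whether a dose meets the 25% limit, as in three of the six comparisons above, but it often does not.

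The figures assume the Table 7.1.1:3 prior and invented data. The protocol defers the final-analysis prior to the SAP, whose visible text does not give it. Dose decisions by the Safety Monitoring Committee are separate, recruitment has stopped and Phase II is cancelled, so the exposure is confined to the final reported MTD. That makes it worth correcting, without suggesting that the reported result is wrong.

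**What to change.** 1. In SAP 5.1 and 7.4, exclude only replaced subjects without a protocol 5.3.1 DLT in the MTD evaluation period. A subject with such a DLT stays in the MTD determination whatever the attribution or replacement status.
2. Rewrite the SAP 6.3 MTD evaluable set to follow protocol 5.3.1, with its 3 administrations and its toxicity-or-tolerability test for DLT-free patients, and name the set in 7.4. Add no condition that 5.3.1 lacks: requiring at least one BI 836858 dose before a DLT counts, or all 3 doses from every DLT-free patient, would create new departures.
3. In the 7.4 listing, flag DLTs with onset before the first BI 836858 administration.
4. Reconcile protocol 3.3.4.1 with 5.3.1 and record the reading used in SAP section 4.

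The cost is a few sentences and one reconciliation note, with no new data. The downside is that the DLT rate used for the MTD may be slightly less favourable. If no patient is affected, the edit only confirms the result.

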7.5 SECONDARY ENDPOINT(S)

Phase I

The secondary endpoint overall response will be listed only. If considered useful, aggregated tables will be provided where different doses might be grouped.

7.7 EXTENT OF EXPOSURE

Standard descriptive analyses over all treatment courses will be performed. This will include a summary of the variables defined in [Section 5.4.1](#) and will comprise a mixture of frequency and percentages, as well as summary statistics.

The time to treatment discontinuation is defined as (date of last administration of trial medication— date of randomisation + 1). Subjects who have not discontinued treatment will be censored at the earliest of the following: date of last administration of trial medication, or date of data cut-off. Subjects who are randomised, but did never receive study medication will be censored on the day of randomisation

A Kaplan-Meier plot of time to treatment discontinuation by treatment group will be presented.

7.8 SAFETY ANALYSIS

All safety analyses will be performed on the treated set.

7.8.1 Adverse Events

The analyses of adverse events (AEs) will be descriptive in nature. All analyses of AEs will be based on the number of subjects with AEs and NOT the number of AEs.

The analyses will be based on BI standards. Adverse events will be coded with the most recent version of MedDRA. The severity of AEs will be scaled according to CTCAE version 4.03.

Reporting will be done according to version 6 of the AE guideline ([8](#)).

For analysis of AE attributes such as duration, severity, etc. multiple AE occurrence data on the CRF, will be collapsed into AE episodes provided that all of the following applies:

- The same MedDRA lowest level term was reported for the occurrences.
- The occurrences were time-overlapping or time-adjacent (time-adjacency of 2 occurrences is given if the second occurrence started on the same day or on the day after the end of the first occurrence).
- Treatment did not change between the onset of the occurrences OR treatment changed between the onset of the occurrences, but no deterioration was observed for the later occurrence.

For each subject, all episodes with the same preferred term (PT) (system organ class, SOC) will be counted only once using a worst case approach for all AE attributes including CTCAE grading.

The analysis of adverse events will be based on the concept of treatment emergent adverse events, where a treatment emergent AE has an onset in the analysing treatment period. All adverse events occurring before first intake of trial medication will be assigned to 'screening' and all adverse events occurring after last intake of trial medication + 30 days will be assigned to 'post-treatment' (in randomized trials for listings only). For details on the treatment definition, see [Section 6.1](#). In addition, a listing will be provided, detailing the actual treatment on the day when the adverse event started.

Adverse events of special interest (AESIs):

Adverse events of special interest (AESIs) are defined in CTP Section 5.3.8.1 as infusion related reactions (IRRs) of CTCAE grade ≥ 3 , DLTs (occurring during the MTD evaluation period or repeated treatment courses), tumor lysis syndrome and drug induced liver injury (DILI).

Other significant AEs:

Other significant AEs are defined as serious and non-serious AEs that lead to dose reduction or permanent discontinuation of study medication. Their incidence will be reported by severity according to CTCAE grades.

An overall summary of adverse events will be presented. This will include the number of subjects with AEs by worst CTCAE grade. The frequency of subjects with adverse events will be summarized by treatment, primary system organ class and preferred term. The system organ classes will be sorted by default alphabetically; preferred terms will be sorted by frequency (within system organ class).

AEs leading to dose reduction, AEs leading to overall permanent discontinuation, DLTs and Adverse events of special interest (AESIs) including Infusion Related Reactions (IRRs) will be tabulated.

Infusion related reactions (IRRs):

IRRs will be the object of special attention.

Subjects with any IRR will be tabulated by treatment and worst CTCAE grade. In addition, the number of infusions and the number of IRRs will be displayed by treatment.

The duration of IRR [h] and the time since start of the respective infusion [min] together with IRR related symptoms will be tabulated by infusion number and overall.

- Duration of IRR [h] = (End time of IRR - Start time of IRR) [seconds] / 3600
- Time since start of the respective infusion [min] = (Start time of IRR - Start time of infusion) [seconds] / 60

The relationship between the occurrence of IRRs and infusion rate as well as the administration of premedication will be examined.

For IRR summary, time since administration of treatment, duration of IRR, and related symptoms will be summarized descriptively by infusion timepoints.

User-defined AE categories (UDAEC)

User-defined AE categories (UDAEC) are defined in Table 7.8.1:1. For UDAECs which contain sub-searches and/or two sensitivity levels (broad and narrow) all possibilities will be displayed on the UDAEC level in tables. For example for UDAEC “Infusion related infections” the tables will include the UDAEC “Infusion related reactions broad” and “Infusion related reactions narrow”. Similarly for UDAEC “Bleeding”, it will include “Bleeding - SMQ Haemorrhage”, “Bleeding - SMQ Haemorrhage laboratory terms broad”, “Bleeding - SMQ Haemorrhage laboratory terms narrow”, “Bleeding - SMQ Haemorrhage terms (excl. laboratory terms) narrow”.

Table 7.8.1:1 Definition of user-defined AE categories

Special Search Category	Definition	Sensitivity
Infusion related reactions (hypersensitivity)	SMQ 20000021 + infusion related reaction PT 10051792	Narrow (Algorithm)
Bleeding	SMQ Haemorrhage 20000038	Narrow & broad
	SMQ Haemorrhage terms (excl. laboratory terms) 20000039	Narrow
	SMQ Haemorrhage laboratory terms 20000040	Narrow & broad
Nausea	BIcMQ Nausea 30000078	Narrow & broad
Vomiting	BIcMQ Vomiting 30000091	Narrow & broad

Table 7.8.1:1 Definition of user-defined AE categories (cont.)

Special Search Category	Definition	Sensitivity
Drug related hepatic disorders	SMQ Drug related hepatic disorders 20000006	Narrow & broad
	SMQ Cholestasis and jaundice of hepatic origin 20000009	Narrow & broad
	SMQ Drug related hepatic disorders - severe events only 20000007	Narrow & broad
	SMQ Liver related investigations, signs and symptoms 20000008	Narrow & broad
	SMQ Liver-related coagulation and bleeding disturbances 20000015	Narrow & broad
ALT	BIcMQ Elevated Specific Liver Function Parameters sub-search1 30000022	Narrow & broad
AST	BIcMQ Elevated Specific Liver Function Parameters sub-search2 30000023	Narrow & broad
ALKP	BIcMQ Elevated Specific Liver Function Parameters sub-search3 30000024	Narrow & broad
gGT	BIcMQ Elevated Specific Liver Function Parameters sub-search4 30000025	Narrow & broad
Bilirubin	BIcMQ Elevated Specific Liver Function Parameters sub-search5 30000026	Narrow & broad
Neutropenia	BIcMQ Neutropenia 30000031	Narrow & broad
Cardiac disorders ¹	SMQ Ischaemic heart disease 20000043	Narrow & broad
	SMQ Cardiac failure 20000004	Narrow & broad
	SMQ Cardiac arrhythmias 20000049	Narrow & broad
Tumour Lysis Syndrome	SMQ Tumour Lysis Syndrome 20000219	All broad
	SMQ Torsade de point/QT prolongation Broad (20000001)	
	SMQ Cardiac arrhythmia terms broad (incl bradyarrhythmias and tachyarrhythmias) (20000050)	
	SMQ Convulsions broad (20000079)	
Fluid accumulation	HLT Total fluid volume increased 10044085	
	HLT Oedema NEC 10030113	

Table 7.8.1:1 Definition of user-defined AE categories (cont.)

Special Search Category	Definition	Sensitivity
	HLT Pulmonary oedemas 10037424	
	HLT Pneumothorax and pleural effusions	
	NEC 10035761	
	PT Ascites 10003445	
	PT Abnormal weight gain 10000188	
Infections	Infections (incl. respiratory infections and sepsis) - SOC 10021881 use label "Infections and infestations"	
	Infections (incl. respiratory infections and sepsis) - HLGT 10024970 use label "Respiratory tract infections"	
	Infections (incl. respiratory infections and sepsis) - HLT 10040054 use label "Sepsis, bacteraemia, viraemia and fungaemia NEC"	
Inflamed gut	PT Enterocolitis 10014893	
	PT Enterocolitis bacterial 10065206	
	PT Enterocolitis fungal 10065205	
	PT Enterocolitis helminthic 10065204	
	PT Enterocolitis infectious 10058838	
	PT Enterocolitis viral 10061841	
	PT Colitis 10009887	
	PT Enteritis 10014866	
Acute febrile neutrophilic dermatosis	PT Acute febrile neutrophilic dermatosis 10000748	

¹ A BIcMQ has been requested, however, as long as this is not available the terms as defined in Table [7.8.1:2](#) will be used.

Table 7.8.1:2 User-defined (sub-) search category of “Cardiac Failure”

Selected PTs for Cardiac Failure
Cardiac asthma
Cardiac failure

Table 7.8.1:2 User-defined (sub-) search category of “Cardiac Failure” (cont.)

Selected PTs for Cardiac Failure
Cardiac failure acute
Cardiac failure chronic
Cardiac failure congestive
Cardiac failure high output
Cardiac index decreased
Cardiac output decreased
Cardiogenic shock
Cardiomegaly
Cardiothoracic ratio increased
Dilatation ventricular
Left ventricular failure
Low cardiac output syndrome
Right ventricular failure
Oedema due to cardiac disease
Left ventricular dysfunction
Ejection fraction decreased
Cardiopulmonary failure
Diastolic dysfunction
Cardiac ventriculogram right abnormal
Cardiac ventriculogram abnormal
Cardiac ventriculogram left abnormal
Cardiac cirrhosis
Right ventricular dysfunction
Ventricular dysfunction
Cardiac resynchronisation therapy
Ventricular failure
Acute left ventricular failure
Acute right ventricular failure
Chronic left ventricular failure
Chronic right ventricular failure
Myocardial depression
Ventricular dyssynchrony
Systolic dysfunction
Neonatal cardiac failure

UDAEC will be summarized by dose cohort, search categories and preferred terms, and CTCAE grade. Some events contribute to more than one UDAEC. Patients with such AEs are counted in each of the UDAEC but are counted only once in the overall number of patients with an AE in any UDAEC.

[Tumor Lysis Syndrome](#)

In patients with a high tumor burden who are exposed to a highly effective therapy, there is a risk of rapid tumor destruction resulting in Tumor Lysis Syndrome (TLS).

Patients will be identified as having potential Tumor Lysis Syndrome if they met **both** of the following two criteria:

- (1) Two or more of the laboratory parameters meet the criteria in [Table 7.8.1:3](#),
 - a. time window
 - i. on the day of BI 836858 infusion or the following 6 days,
 - ii. at least two of the qualifying lab values must have occurred with the same 24 hour period
- (2) Have an adverse event identified by any of the SMQ in [Table 7.8.1:4](#) or have a qualifying creatinine value
 - a. Time windows: AE onset or creatinine observation at any time during the treatment or residual effect periods

Table 7.8.1:3 Laboratory Signs of Cell Destruction

Laboratory parameter	Abnormal value
Uric acid	$\geq 476 \mu\text{mol/L}$ AND increase from relative baseline ¹ by $\geq 25\%$
Potassium	value $\geq 6.0 \text{ mmol/L}$ AND relative baseline $< 6.0 \text{ mmol/L}$
Inorganic phosphate	$\geq 1.45 \text{ mmol/L}$ AND increase from relative baseline by $\geq 25\%$
Calcium	$< 7 \text{ mg/dL}^2$ AND decrease from relative baseline by $\geq 25\%$

¹Relative baseline is derived separately for each BI 836858 infusion as the last value prior to that BI 836858 infusion. Relative baseline will be derived independently for the four parameters, ie. four baseline values do not necessarily have to be derived from the same laboratory assessment.

²For calcium, $0.25^* \text{ mg/dL} = \text{mmol/L}$

Table 7.8.1:4 Clinical Signs of Cell Destruction

Criterion
TLS broad SMQ [20000219]

Table 7.8.1:4 Clinical Signs of Cell Destruction (cont.)

Criterion
Torsade de point/QT prolongation broad SMQ [20000001]
Cardiac arrhythmia terms broad SMQ (incl bradyarrhythmias and tachyarrhythmias) [20000050]
Convulsions broad SMQ [20000079]
Creatinine Absolute increase from relative baseline by 26.5 µmol/L AND increase from relative baseline by $\geq 50\%$

For AEs during the post-treatment period, only subjects with drug related serious adverse event and protocol-specified AEs of special interest by treatment will be presented in listing.

